**7.1.5. Statistical Analyses / Methods**

Details of the planned displays are provided in [Appendix 10: List of Data Displays](#) and will be based on GSK data standards and statistical principles.

Unless otherwise specified, endpoints / variables defined in Section 7.1.1 will be summarised using descriptive statistics, graphically presented (where appropriate) and listed.

**7.1.5.1. Statistical Methodology Specification**

Endpoint

 
Percentage of participants with zero errors after 28 days of use
 

Model Specification

 
The primary endpoint of the percentage of participants with zero errors after 28 days of use, will be analysed using the Intent-to-treat population.
 
This endpoint will be analysed using conditional logistic regression with subject as fixed strata, and treatment option and period as fixed effects.
 
If there are low cell counts (<5) in the cross tabulation of subjects making errors on ELLITPA compared to DISKUS + HandiHaler or the model fails to converge with all cell counts >=5, then the exact conditional logistic regression with subject as fixed strata, and treatment option and period as fixed effects will be used instead.
 

Model Checking & Diagnostics

 
None
 

Model Results Presentation

 
The odds ratio, 95% CI and p-value will be presented for the comparison between treatment options. It will be based on a two-sided hypothesis testing approach of superiority.
 

Sensitivity and Supportive Analyses

 
A sensitivity analysis will be performed using the Cochran-Mantel-Haenszel (CMH) test. The CMH test serves as a stratified approximation to the Mainland-Gart test, a variation of a one-sample chi-square test that accounts for study inhaler sequence (period). A subject who had an error with both devices or who had no errors with both devices does not provide any information about the superiority of either device. Only those subjects who had error(s) in one device and had no error in the other device are counted for in the Mainland-Gart test.
 
For the supplementary estimand a tipping point analysis will be performed to assess how robust the composite estimand is to missing data assumptions. To assess this the outcomes for subjects with missing error assessment in period 2 will be varied in the two treatment groups independently from imputing 0 subjects with an error to all subjects with an error.
 

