7.3. Method of Treatment Assignment

All participants will be centrally randomized using an Interactive Web Response System (IWRS). Before the study is initiated, the log in information and directions for the IWRS will be provided to each site.

Participants will be assigned in equal numbers to one of the following sequences. The possible sequences are shown below:

Randomization Group	Sequence of Using the Inhalers		Preference Questionnaire Version
	1 st Period	2 nd Period	
A	ELLIPTA	DISKUS + HandiHaler	1
B	ELLIPTA	DISKUS + HandiHaler	2
C	DISKUS + HandiHaler	ELLIPTA	1
D	DISKUS + HandiHaler	ELLIPTA	2

Study treatments will be dispensed at the study visit summarized in the SoA.

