10.2. Sample Size Determination

The sample size calculations for this study have been based on the primary endpoint, which is the percentage of participants making zero errors in each treatment group (ELLIPTA or DISKUS + HandiHaler) after 28 days use.

The estimates of inhaler errors were taken from the overall errors reported in the 200301 study for each individual inhaler (ELLIPTA, DISKUS and HandiHaler) separately. Although this study is only assessing combined errors in the DISKUS + HandiHaler treatment group, individual inhaler errors were used to estimate the combined error rate in order to provide a conservative estimate. By doing this it assumes that participants, who made no errors on the DISKUS inhaler, would not make any errors of the HandiHaler inhaler and vice-versa.

As the 200301 study only had a single visit, no estimates were available for error rates over 28 days, however the study did provided estimates of participant errors after reading the PIL and after being instructed on correct use by a HCP up to three times. As participants will have the PIL for 28 days, and can be instructed by a HCP at the inhaler dispensing visit if necessary, both estimates of error rates along with a sensitivity analysis examining some of the potential error rates between were used to inform sample size calculations.

Using 10,000 simulations, a total of 216 participant (54 per treatment sequence) provide at least 90% power to show a statistically significance difference between the overall error rate of the ELLIPTA inhaler versus DISKUS + HandiHaler inhalers, for all of the paired treatment error rates shown in [Table 1](#).

Table 1 Error rates of ELLIPTA vs. DISKUS + HandiHaler achievable with 90% power, 5 % Type 1 error using a total of 216 participants

ELLIPTA Error Rate	DISKUS + HandiHaler Error Rate
33%	>=50%
30%	>=47%
20%	>=35%
10%	>=23%
5%	>=15%

Conditional logistic regression and a two-sided 5% significance level were used as the analysis method for all simulations performed. As it is expected that some participants would drop out or change inhalers during the study, with 10% withdrawal it would be

necessary to enrol 240 participants (60 per treatment sequence) to ensure there were 216 participants with evaluable data at the end of the study.

For the purpose of this study an evaluable participant is defined as a randomized participant who completed error assessments for both randomized treatment groups.

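### The switch to exact conditional logistic regression can be set off by concordant cells that the model does not use, at a modest and avoidable cost in power when error rates are low

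*SAP*

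**What the plan says.** SAP 7.1.5.1 analyses zero errors after 28 days by conditional logistic regression, with participant as stratum and treatment and period as effects. It moves to the exact version if counts below 5 appear "in the cross tabulation of subjects making errors on ELLITPA compared to DISKUS + HandiHaler or the model fails to converge". Nothing limits the rule to particular cells of that table.

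The same box plans a Cochran-Mantel-Haenszel sensitivity analysis. It explains that participants with the same result on both devices tell us nothing about which is better: "Only those subjects who had error(s) in one device and had no error in the other device are counted for in the Mainland-Gart test".

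The rule reaches further than the primary endpoint. SAP 7.2.5.1 refers back to it for critical errors. SAP 7.3.5.1 repeats it for the maintenance-inhaler model and refers back to it for errors after reading the leaflet.

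Protocol 10.2 gives the power claim: "Using 10,000 simulations, a total of 216 participant (54 per treatment sequence) provide at least 90% power" for each pair of rates in Table 1. Of the method it says: "Conditional logistic regression and a two-sided 5% significance level were used as the analysis method for all simulations performed". It mentions no exact fallback.

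**The concern.** Conditional logistic regression with one pair per participant conditions on that participant's total. Pairs with no error on either device, or an error on both, contribute a constant. The trigger nevertheless counts them. Two trials with identical informative data could then report different primary results because one had four participants who erred on both devices and the other had five.

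The direction of the effect is known. The exact test is conservative, so an unnecessary switch costs power and widens the interval. When error rates are low the both-error cell is the smallest of the four, so it is the cell most likely to set off the switch.

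**Working it through.** **Inputs.** 216 evaluable participants, two-sided 5% and the five pairs of rates come from Protocol 10.2. There are 108 participants per device sequence (Protocol 5.2), with equal allocation (Protocol 7.3). Assumed, because the documents give neither: no period effect, and errors on the two options independent within a participant unless a correlation is stated.

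**What the model uses.** Label the discordant counts as follows.
- ELLIPTA first: *a* with an error on ELLIPTA only, *b* with an error on DISKUS + HandiHaler only.
- DISKUS + HandiHaler first: *c* with an error on ELLIPTA only, *d* with an error on DISKUS + HandiHaler only.

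With treatment and period in the model, the log odds ratio for an error is ½ ln(*ac*/*bd*), and the Wald statistic is z = ln(*ac*/*bd*) / √(1/*a* + 1/*b* + 1/*c* + 1/*d*). The exact version is Fisher's test on sequence by period of the error, with rows (*a*, *b*) and (*d*, *c*). No concordant count appears in either.

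**Illustration.** Take *a* = 6, *b* = 14, *c* = 7, *d* = 13. Then z = ln(42/182) / √(0.1667 + 0.0714 + 0.1429 + 0.0769) = −1.466/0.677 = −2.17, p = 0.030. Fisher's test gives p = 0.056. The discordant totals are 13 and 27. If five participants err on both devices the plan reports the first p-value; if four do, it reports the second.

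**The plan's own power.** Simulated power of asymptotic conditional logistic regression (at least 20,000 trials per row) is 94.9%, 95.2%, 93.7%, 95.4% and 92.0% for 33/50, 30/47, 20/35, 10/23 and 5/15. The claim of at least 90% reproduces in every row.

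**How often the trigger fires.** Expected both-error count = 216 × (ELLIPTA rate) × (DISKUS + HandiHaler rate).

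| Rates | Expected both-error count | Switch caused by a concordant cell alone |
|---|---|---|
| 33/50 | 216 × 0.33 × 0.50 = 35.6 | 0% |
| 30/47 | 216 × 0.30 × 0.47 = 30.5 | 0% |
| 20/35 | 216 × 0.20 × 0.35 = 15.1 | 0.1% |
| 10/23 | 216 × 0.10 × 0.23 = 5.0 | about 45% |
| 5/15 | 216 × 0.05 × 0.15 = 1.6 | about 92% |

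At 5/15 the rule fires for any reason in 97.8% of trials.

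**Power under the two triggers** (30,000 trials per scenario; tables with a zero sequence-by-direction cell go to the exact test). The SAP does not define the exact p-value, so both common forms are shown.

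| Rates, correlation | SAP rule, twice the smaller tail | SAP rule, probability-ordered | Discordant-only trigger |
|---|---|---|---|
| 10/23, 0 | 94.4% | 95.0% | 95.7% |
| 5/15, 0 | 89.4% | 91.5% | 93.7% |
| 5/15, 0.1 | 93.1% | 94.5% | 95.8% |
| 5/15, 0.2 | 96.4% | 97.0% | 97.5% |
| 5/15, 0.3 | 98.2% | 98.5% | 98.5 to 98.6% |

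At 10/23 with correlation 0.2 the rules agree (98.4%). The other three rows of Table 1 are essentially unchanged.

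**Type I error.** With both rates at 5%, 10% or 15% and correlations from 0 to 0.4, the discordant-only trigger gave between 1.1% and 4.9%. With both rates at 10%, the SAP rule gave about 2.5 to 3.5%.

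**The case against.** The best defence is that the rule is pre-specified, errs on the safe side and costs little. Three parts of it stand.

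First, a reader might infer that the trial falls short of its planned power. The documents do not support that. A figure below 90% needs the lowest row of Table 1, zero correlation and a doubled-tail exact p-value all at once, and even then the shortfall is about half a point. The probability-ordered version stays above 90%, and so does either version at a correlation of 0.1. Some positive correlation is plausible, since each participant serves as his or her own control. The protocol's power also rests on plain conditional logistic regression, which gives about 92.0% at 5/15. The probability-ordered SAP rule, at 91.5%, is only half a point below that.

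Second, a reader might infer that the exact test is pointless whenever a concordant cell sets it off. That is too strong. Because period is in the model, inference rests on four sequence-by-direction counts. Among switches caused by a concordant cell alone, at least one of those four is below 5 in about 75% of trials at 5/15, though in only 14% at 10/23. What can be said is that the sparse tables did not push type I error above 5% in the scenarios tried.

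Third, the effect on critical errors cannot be sized. No planning rate is given for them and no power is claimed. If they are rarer than overall errors, the trigger would tend to fire more often there.

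None of this explains why a cell outside the likelihood should choose the analysis.

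**Conclusion.** The trigger is mis-specified: it depends on counts that the model ignores and that the SAP itself says are uninformative. The consequence is an avoidable, modest loss of power. At independence it is about 2 to 4 points at 5/15 and about 1 point at 10/23. At a correlation of 0.2 it is 0.5 to 1 point at 5/15 and nil at 10/23. In the other three planning rows it is negligible.

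The protocol's statement that 216 participants "provide at least 90% power to show a statistically significance difference" is not clearly contradicted, and the rule does not inflate type I error. Severity is minor. The sizes rest on no period effect, on the assumed correlations and on the exact p-value chosen. The defect in the wording rests on none of these.

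**What to change.** Before database freeze, reword the trigger in SAP 7.1.5.1. Exact conditional logistic regression is used only if one of these holds:
- the number with an error on ELLIPTA only, or with an error on DISKUS + HandiHaler only, is below 5;
- any of the four sequence-by-direction discordant cells is zero;
- the model fails to converge.

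State which exact p-value applies (twice the smaller tail or probability-ordered). Carry the same wording into 7.2.5.1 and 7.3.5.1.

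The cost is a sentence or two of text. The small downside is that large-sample inference would be used in some tables that are sparse once split by sequence. Type I error was checked and held; interval coverage was not.

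A more cautious alternative is to trigger on the discordant counts by sequence. At independence it gives 92.0 to 92.9% at 5/15 and 95.6 to 95.7% at 10/23, so it keeps part of the gain. With correlated errors it may keep none: at 5/15 and correlation 0.2, some sequence-by-direction cell is below 5 in about 97% of trials, whereas the present rule fires in about 62%. Either choice removes the concordant cells from the decision.

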## **7.2. Secondary Efficacy Analyses**

### **7.2.1. Endpoint**

- 1) Percentage of participants with zero critical errors after 28 days of use.
- 2) Number of errors by type for each inhaler after 28 days use
- 3) Number and change in errors per participant for each treatment group (V2 and V3) after 28 days use
- 4) Number and change in errors for each treatment group in participant with one or more errors after 28 days use

### **7.2.2. Summary Measure**

- 1) Odds ratio
- 2) Summary statistics
- 3) Summary statistics
- 4) Summary statistics

### **7.2.3. Population of Interest**

The secondary efficacy analyses will be based on the Intent-To-Treat population, unless otherwise specified.

### **7.2.4. Strategy for Intercurrent (Post-Randomization) Events**

As these are secondary endpoints only the primary estimand will be assessed.

### **7.2.5. Statistical Analyses / Methods**

Details of the planned displays are provided in [Appendix 10: List of Data Displays](#), and will be based on GSK data standards and statistical principles.

Unless otherwise specified, endpoints / variables defined in Section [7.2.1](#) will be summarised using descriptive statistics, graphically presented (where appropriate) and listed.

The following secondary endpoints will be summarised only:

- Number of errors by type for each treatment group after 28 days of use.
- Number and change in errors per participant for each treatment group (V2 and V3) after 28 days of use.
- Number and change in errors for each inhaler in participants with one or more errors after 28 days of use.

**7.2.5.1. Statistical Methodology Specification**

Endpoint / Variables

 
Percentage of participants with zero critical errors after 28 days of use
 

Model Specification

 
See Section 7.1.5.1.
 

Model Checking & Diagnostics

 
See Section 7.1.5.1.
 

Model Results Presentation

 
See Section 7.1.5.1.
 

Sensitivity and Supportive Analyses

 
See Section 7.1.5.1.
 

**7.3. Exploratory Efficacy Analyses****7.3.1. Endpoint**

- 1) Comparison of correct inhaler use as defined by the percentage of participants with zero errors after 28 days of use, including the number of prescribed maintenance inhalers as a covariate.
- 2) The comparison of participants making zero errors after reading the PIL (s) at the start of each treatment period.
- 3) Inhaler preference based on how easy it was to tell how many doses remain.
- 4) Inhaler dosing regimen preference.
- 5) Inhaler regimen preference based on the number of steps needed to take the medication.

**7.3.2. Summary Measure**

- 1) Odds ratio and p-value for interaction
- 2) Odds ratio
- 3) Summary statistics and p-value
- 4) Summary statistics and p-value
- 5) Summary statistics and p-value

**7.3.3. Population of Interest**

The secondary efficacy analyses will be based on the Intent-To-Treat population, unless otherwise specified.

**7.3.4. Strategy for Intercurrent (Post-Randomization) Events**

As these are exploratory endpoints only the primary estimand will be assessed.

### 7.3.5. Statistical Analyses / Methods

Details of the planned displays are provided in [Appendix 10: List of Data Displays](#) and will be based on GSK data standards and statistical principles.

Unless otherwise specified, endpoints / variables defined in Section [7.2.1](#) will be summarised using descriptive statistics, graphically presented (where appropriate) and listed.

#### 7.3.5.1. Statistical Methodology Specification

Endpoint / Variables

 
Comparison of correct inhaler use as defined by the percentage of participants with zero errors after 28 days of use, including the number of prescribed maintenance inhalers as a covariate.
 

Model Specification

 
The primary endpoint of the percentage of participants with zero errors after 28 days of use, will be analysed using the Intent-to-treat population.
 
This endpoint will be analysed using conditional logistic regression with subject as fixed strata. Treatment option, number of COPD maintenance devices and period will be fixed effects.
 
Two models will be analysed. The first will contain the number of COPD maintenance devices and treatment option, whilst the second will include the interaction term between the number of COPD maintenance devices and treatment option.
 
If there are low cell counts (<5) in the cross tabulation of subjects making errors on ELLITPA compared to DISKUS + HandiHaler or the model fails to converge with all cell counts >=5, then the exact conditional logistic regression with subject as fixed strata, and treatment option and period as fixed effects will be used instead.
 

Model Checking & Diagnostics

 
See Section 7.1.5.1.
 

Model Results Presentation

 
See Section 7.1.5.1. In addition, for the interaction model the p-value for the interaction will also be produced.
 

Sensitivity and Supportive Analyses

 
No sensitivity analysis will be performed.
 

Endpoint / Variables

 
The comparison of participants making zero errors after reading the PIL (s) at the start of each treatment period
 

Model Specification

 
See Section 7.1.5.1.
 

Model Checking & Diagnostics

 
See Section 7.1.5.1.
 

Model Results Presentation

 
See Section 7.1.5.1.
 

Sensitivity and Supportive Analyses

 
No sensitivity analysis will be performed.
 

Endpoint / Variables

 
Inhaler preference based on how easy it was to tell how many doses remain.
 
Inhaler dosing regimen preference.
 
Inhaler regimen preference based on the number of steps needed to take the medication.
 

Model Specification

 
The endpoint of treatment preference will be analysed using the Intent-to-treat population.
 
This endpoint will be analysed using the Cochran-Mantel-Haenszel test.
 

Model Checking & Diagnostics

 
None.
 

Model Results Presentation

 
The percentage of preference for each specific attribute (i.e., preferring ELLIPTA inhaler, preferring DISKUS + HandiHaler, and no preference) will be summarised by inhaler use sequence.
 
Subject preference will also be analysed using a Cochran-Mantel-Haenszel test. The Cochran-Mantel-Haenszel test serves as a stratified approximation to Prescott's test, a variation of a one-sample chi-square test that accounts for study inhaler sequence and subjects who indicate no preference. P-values from this analysis will be presented in summary and analysis tables.
 

Sensitivity and Supportive Analyses

 
No sensitivity analysis will be performed.
 

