### 5.3. Examination of Covariates, Other Strata and Subgroups

#### 5.3.1. Covariates and Other Strata

The list of covariates and other strata may be used in descriptive summaries and statistical analyses. Additional covariates and other strata of clinical interest may also be considered.

Category	Covariates and / or Subgroups
Number of prescribed maintenance inhalers	This will be included as a covariate in the model to examine whether additional background inhalers impact error rates. Number of prescribed maintenance inhalers will be fitted as a categorical variable.

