2.16	ITT	EFF_T04	Analysis of Percentage of Participants with Zero	Include an additional row for	SAC

Overall Summary of Errors					
No.	Population	IDSL / TST ID / Example Shell	Title	Programming Notes	Deliverable
			Errors after 28 Days of Use, including the Number of Prescribed Maintenance Inhalers as a Covariate (Interaction Model).	the p-value of the interaction between number of prescribed maintenance Inhalers and treatment option.	
2.17	ITT	EFF_T04	Analysis of Participants making Zero Errors after Reading the PIL (s) at the Start of Each Treatment Period.		SAC
2.18	ITT	EFF_T03	Summary and Analysis of Treatment Preference		SAC
2.19	ITT	EFF_T03	Summary of Treatment Preference by Age	This is a summary table only so do not include any analysis. Use age categories: 40-64, 65-74 and $\geq 75$	SAC

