DISKUS + HandiHaler	XXX (XX%)	
No Preference	XXX (XX%)	

Note: The p-value is from the Cochran-Mantel-Haenszel Test.  
Programming notes: %'s calculated out of the small n for each question.

Example : EFF\_T04  
Protocol : 206901  
Population : Intent to Treat

Table X.X  
Analysis of Percentage of Participants making Zero Errors after 28 days use

	ELLIPTA (N=XXX)	DISKUS + HandiHaler (N=XXX)
Zero Errors	XXX (XX%)	XXX (XX%)
At Least one Error	XXX (XX%)	XXX (XX%)
ELLIPTA vs DISKUS + HandiHaler		
Odds Ratio	X.XX	
95% CI	(X.XX, X.XX)	
p-value	X.XXX	

Note: Odds ratio, 95% CI and p-value obtained from a conditional logistic regression model. Subject is included in the model as fixed strata, treatment option and period included as fixed effects.

Example : EFF\_T06  
Protocol : 206901  
Population : Intent to Treat

Table X.X  
Summary of Overall Errors

	Total (N=XXX)
Zero Errors on ELLIPTA	XXX (XX%)
At least one Error on ELLIPTA	XXX (XX%)
Zero Errors on DISKUS + HandiHaler	XXX (XX%)
At least one Error on DISKUS + HandiHaler	XXX (XX%)
Zero Errors on ELLIPTA or DISKUS + HandiHaler	XXX (XX%)
At least one Error on ELLIPTA and DISKUS + HandiHaler	XXX (XX%)
Number of subjects with discordant results [1]	XXX (XX%)
At least one Error on ELLIPTA and Zero Errors on DISKUS + HandiHaler [2]	XXX (XX%)
At least one Error on DISKUS + HandiHaler and Zero Errors on ELLIPTA [2]	XXX (XX%)

[1] Defined as an error in one device and not the other.

[2] Percentage is out of the number of subjects with discordant results.

Example : EFF\_T07  
Protocol : 206901  
Population : Intent to Treat

Table X.X  
Sensitivity Analysis of Percentage of Subjects making Zero Errors

	Result
-----	
Overall Errors	
Number of subjects with discordant results [1]	XXX
Number of subjects with an error on ELLIPTA	XXX (XX%)
Number of subjects with an error on DISKUS + HandiHaler	XXX (XX%)
p-Value [2]	
Critical Errors	
Number of subjects with discordant results [1]	XXX
Number of subjects with a critical error on ELLIPTA	XXX (XX%)
Number of subjects with a critical error on DISKUS + HandiHaler	XXX (XX%)
p-Value [2]	X.XXX

[1] Defined as an error in one device and not the other.

[2] Analysis performed using the Cochran-Mantel-Haenszel test

Note: Subjects are only included in the analysis if they have discordant data.

Example : EFF\_T08  
Protocol : 206901  
Population : Intent to Treat

Table X.XX  
Summary of Number and Change in Errors per Participant in Each Treatment Group

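### Table 2.16 takes a single ELLIPTA vs DISKUS + HandiHaler odds ratio from an interaction model, where its meaning depends on unstated coding, and no planned display shows how the device effect varies by number of maintenance inhalers

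*SAP*

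**What the plan says.** SAP 7.3.5.1 plans two conditional logistic regressions for the first exploratory endpoint, with participant as stratum: "Treatment option, number of COPD maintenance devices and period will be fixed effects". The first has no interaction, "whilst the second will include the interaction term between the number of COPD maintenance devices and treatment option". SAP 5.3.1 adds: "Number of prescribed maintenance inhalers will be fitted as a categorical variable". No reference level, parameterisation or averaging weights are stated.

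For results, 7.3.5.1 refers back to 7.1.5.1: "The odds ratio, 95% CI and p-value will be presented for the comparison between treatment options". The one addition is: "In addition, for the interaction model the p-value for the interaction will also be produced". SAP 7.3.2 gives the summary measure as "Odds ratio and p-value for interaction".

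Table 2.16 (SAP 10.10.5) uses shell EFF_T04, and its programming note adds one row for "the p-value of the interaction between number of prescribed maintenance Inhalers and treatment option". The shell (Appendix 11) has one comparison, headed "ELLIPTA vs DISKUS + HandiHaler", with one odds ratio, one interval and one p-value. Its footnote describes a model with treatment and period only.

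The objective (Protocol 4, SAP 2.2) is to assess the impact of the number of maintenance inhalers on study inhaler errors.

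**The concern.** Once treatment interacts with a categorical factor, the model has one device odds ratio per category and no single one. Under reference coding, the treatment coefficient is the effect in whichever category the programmer makes the reference. Under effect coding, it is the plain mean of the category log odds ratios, so a small category counts as much as a large one. The shell prints either under the same unqualified heading as the primary result, with a footnote describing a different model.

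Two things are at stake. A reader may compare Table 2.16 with Table 2.06 as though both estimated the same quantity. And the objective is left with an interaction p-value but no estimate of how the device effect changes. SAP 10.10.5 breaks errors down by age (Table 2.04) but not by inhaler count. The model without interaction does not fill the gap: the count is fixed at randomisation (SAP 10.6.2.3), so its main effect is constant within participant and drops out of the conditional likelihood.

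**Working it through.** **1. The plan's own figure.** Protocol 10.2 states at least 90% power with 216 evaluable participants for every pair in its Table 1 (two-sided 5%, conditional logistic regression). Simulating 10,000 trials per pair, with errors on the two regimens independent within participant (an assumption), gives 94.6%, 95.3%, 93.9%, 95.5% and 91.7%. Enrolment is 216/(1 − 0.10) = 240. Both agree with the plan.

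**2. What the row estimates.** With two periods, only discordant participants contribute. Let e and d be the error probabilities on ELLIPTA and DISKUS + HandiHaler. The odds ratio for zero errors is (1 − e)d / [e(1 − d)]. Take e = 33% throughout, and d = 40% in 60% of participants and 65% in the other 40% (assumed):

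- First category: 0.67 × 0.40 / (0.33 × 0.60) = 0.268/0.198 = 1.35.
- Second category: 0.67 × 0.65 / (0.33 × 0.35) = 0.4355/0.1155 = 3.77.
- Effect coding: √(1.35 × 3.77) = 2.26.
- Model without interaction: (0.6 × 0.268 + 0.4 × 0.4355) / (0.6 × 0.198 + 0.4 × 0.1155) = 0.335/0.165 = 2.03.

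Simulated medians are 1.36, 3.86, 2.31 and 2.05. In one simulated data set of 216 from this scenario, the treatment row was 1.50 (p = 0.087), 3.36 (p = 0.0008) or 2.24 (p = 0.0002), depending only on coding. The interaction p-value was 0.064 each time. The model without interaction gave 1.96 (p = 0.0005).

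**3. Rejection rate with the same device effect in every category.** Ignoring the period term, SE = √{1/[n(1 − e)d] + 1/[n e(1 − d)]} and power ≈ Φ(log OR/SE − 1.96), where n is the number in the reference category.

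At 33/50, log OR = ln(0.335/0.165) = 0.708. For n = 216, SE = √(1/72.36 + 1/35.64) = 0.205, so power ≈ Φ(1.50) = 93%. For n = 108, SE = 0.289, so power ≈ Φ(0.49) = 69%.

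At 20/35, log OR = ln(0.28/0.13) = 0.767. SE = 0.228 at n = 216 (92%) and 0.323 at n = 108 (66%).

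| Reference share (assumed) | 33/50, by hand | 20/35, by hand | Simulated |
|---|---|---|---|
| Primary model (all 216) | 93% | 92% | 94% at both |
| 70% | 83% | 80% | 83–84% |
| 50% | 69% | 66% | 71% and 68% |
| 30% | 47% | 45% | 46–47% |

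Under effect coding with two equal halves, the variance of the mean is (0.289² + 0.289²)/4 = 0.0418, which is the primary model's 0.205² = 0.042 up to rounding, so little is lost. With an 80/20 split at 33/50, the effect-coded row simulates at 83% against 95%.

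**4. Opposite effects.** Take 33/50 in one half and 50/33 in the other. Each regimen's error rate is (33 + 50)/2 = 41.5%, so there is no overall difference. The reference-coded row rejects in about 70% of trials and the primary model in about 5%. The interaction p-value is below 0.05 in about 95%.

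**5. Where the interaction model is not fitted.** SAP 7.3.5.1 switches to an exact model with treatment and period only if a cell of the cross-tabulated errors is below 5 or the model does not converge. The expected count with errors on both regimens is 216 × 0.05 × 0.15 = 1.6 at 5/15 and 216 × 0.10 × 0.23 = 5.0 at 10/23. Reading the rule as covering all four cells, the switch occurs in about 98% of trials at 5/15, about 43% at 10/23, and under 0.1% at 33/50 and 20/35 with two equal categories.

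**The case against.** The strongest reply is that nothing depends on this row. The analysis is exploratory, the primary comparison is in Table 2.06, and the study is sized only for the primary endpoint, so no power standard applies here. The interaction p-value, which bears most directly on the objective, does not depend on coding and sits in the same table. All of that stands, and it limits the weight of the point.

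Three stronger readings are tempting, and the documents do not support them.

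- A reader might infer that the SAP presents the row as the overall device comparison. It does not use that word, the Table 2.16 title identifies the interaction model, and the null hypothesis in SAP 2.4 is stated for the primary endpoint. The row is unqualified, not expressly mislabelled.
- A reader might infer severe losses at low error rates. Ignoring the fallback gives 64% against 92% at 5/15 with a 50% reference. With the four-cell rule applied, and the asymptotic p-value standing in for the exact one, the row rejects in about 90% of trials against 91%. If only discordant cells counted, the switch would occur in about 5% of trials at 5/15; the SAP does not limit the rule that way.
- A reader might infer that a false overall effect would go unnoticed. The 70% figure needs exactly opposite effects in equal halves, and the interaction p-value flags that case in about 95% of trials.

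None of this supplies a meaning for the printed odds ratio when the interaction model is fitted, or an estimate by number of inhalers.

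**Conclusion.** The point holds as a reporting gap in one exploratory table. As specified, Table 2.16 gives an odds ratio, interval and p-value whose meaning depends on unstated coding, and no display answers the objective with an estimate. Where the interaction model is fitted, the loss against the primary model under a common effect and reference coding runs from about 10 points (70% reference) to nearly 50 (30% reference). It is small for balanced effect coding. These sizes rest on assumed category shares, independent outcomes within participant, 216 completers and the 33/50 and 20/35 pairs. They do not carry over to 5/15, nor to the roughly 43% of trials at 10/23 in which the fallback applies. The primary analysis, its power and the sample size are not affected.

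**What to change.** In SAP 7.3.5.1 and the Table 2.16 programming note, replace the single odds ratio, interval and p-value with the device odds ratio and 95% CI for each inhaler-number category from the interaction model, plus the interaction p-value. State that the overall comparison is taken only from Table 2.06. Correct the shell footnote for this table so that it describes the interaction model. Fix a rule for pooling sparse categories before analysis; the documents give no distribution from which to choose a cut-point, so that choice is the sponsor's.

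The cost is a few lines of SAP text and one modified shell, with no new data. The category intervals will be wide, and pooling loses detail at the highest counts.
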